clinical significant.

### **9.5.2 Appropriateness of Measurements**

The measurements used in this study were considered appropriate for the indication studied. Disease response is a common tool used in cancer trials to study the effectiveness of the study drug. Safety and tolerability of the study drug were reported during the trial.

### **9.5.3 Primary Efficacy Variable(s)**

The primary efficacy endpoint was the Objective response rate (ORR), defined as complete response (CR) + partial response (PR), according to RECIST v1.1 criteria

### **9.5.4 Drug Concentration Measurements**

Pharmacokinetic measurement was only performed on subjects enrolled in Stage I.

- PK blood samples were taken immediately pre-infusion then at 24, 25, 26, 28 and 32 hours after start of infusion on Days 1 and 8 of Cycle 3 if dose level of Cycle 3 is 24 mg/m^2 (time window at each sample collected: ±5 min).
- Blood samples were collected, using 10 mL sodium heparin Vacutainer® tubes. The tube was gently inverted to ensure adequate mixing of the blood sample and anticoagulant. Samples were placed on ice until separation and must be centrifuged within 20 minutes of collection. A precise record of blood sample collection times must be maintained on the appropriate source document.
- Plasma samples were analyzed via a validated high performance liquid chromatography/tandem mass spectrometry (HPLC/MS-MS) method for SCB01A.

## **9.6 DATA QUALITY ASSURANCE**

The Sponsor or its designee performed the quality assurance and quality control activities of this study; however, responsibility for the accuracy, completeness, and reliability of the study data presented to the Sponsor lies with the investigator generating the data.

Audits may be conducted at the discretion of the Sponsor as part of the implementation of quality assurance to ensure that the study is being conducted in compliance with the protocol, SOPs, GCP, and all applicable regulatory requirements. Audits were independent of and separate from the routine monitoring and quality control functions. If such an audit occurred, the investigator must agree to allow access to required subject records. By signing this protocol, the Investigator granted permission to personnel from the Sponsor, its representatives, and appropriate regulatory authorities for on-site monitoring of all appropriate study documentation, as well as on-site review of the procedures employed in CRF generation, where clinically appropriate.

## **9.7 STATISTICAL METHODS PLANNED IN THE PROTOCOL AND DETERMINATION OF SAMPLE SIZE**

### **9.7.1 Statistical and Analytical Plans**

#### **9.7.1.1 Populations for Analysis**

Study subjects were categorized into the following populations for analysis:

- Intention-to-treat (ITT) population: The ITT population consisted of all subjects enrolled in the study and received at least one study treatment.

- Per-protocol (PP) population: The PP population consisted of all subjects who (1) withdrew from study for DLT, or (2) completed at least 3 cycles of study treatment regimen, have measurable baseline disease and, at least, one post-baseline RECIST assessment (PD, SD, PR or CR). Subjects with a major protocol deviation or AE, deemed by the Medical Monitor to have an impact on the study endpoints, would be excluded from the PP population.
- PK population: The PK population consisted of all subjects in stage I who received, at least, one dose of 24 mg/m^2 of SCB01A with sufficient post-dose bio-samples collected for PK profile characterization.

Details of any other populations for analysis were described in the statistical analysis plan (SAP).

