- a) Dose de-escalation: if any DLT experienced before Cycle 2 Day 8, the dose will be de-escalated to Dose 2a (15 mg/m²) for Cycle 2 Day 8. If first DLT during Cycle 2 is experienced after Cycle 2 Day 8, the dose will be de-escalated to Dose 2a (15 mg/m²) for Cycle 3. If no DLT is observed in Dose 2a, the subjects will receive the Dose 2a until PD, consent withdraw or death. Once more dose de-escalation (Dose 2b, 12 mg/m²) will be allowed if another DLT is observed in Dose 2a.
- b) Dose maintained: If clinical benefit observed at Dose 2 and without DLT, the Dose 2 can be continued until PD, intolerable toxicity, consent withdraw or death.
- 3. Dose 3 (24 mg/m²), will be administrated for one cycle and safety and tumor assessment will be performed prior to drug administration on Cycle 4 Day 1.
 - a) Dose de-escalation: if any DLT experienced before Cycle 3 Day 8, the dose will be de-escalated to Dose 3a (20 mg/m²) for Cycle 3 Day 8. If first DLT during Cycle 3 is experienced after Cycle 3 Day 8, the dose will be de-escalated to Dose 3a (20 mg/m²) for Cycle 3. If no DLT is observed in Dose 3a, the subjects will receive the Dose 3a until PD, consent withdraw or death. Once more dose de-escalation (Dose 3b, 16 mg/m²) will be allowed if another DLT is observed in Dose 3a.

Figure 2: Dose Modification

If the subject experienced any neurotoxic DLT, the subject will be withdrawn.

Per-protocol (PP) subjects will be considered to be evaluable for ORR conclusion; Non-evaluable subjects will be replaced.

Simon’s Two-Stage Design¹

Stage I: A total of up to 10 evaluable subjects will be enrolled for Stage I to receive at least 3 cycles of i.v. administration by 24-hours infusion of SCB01A. The tumor response review will be

Name of Sponsor/Company: SynCore Biotechnology Co. Ltd.	
Name of Study Product: SCB01A	
Protocol Number: SCB01A-22	Indication: Recurrent or metastatic squamous cell carcinoma of head and neck

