End of study will be either 12 months after the 1st treatment with SCB01A or end of 27 weeks survival follow-up, whichever comes later.

Data and Safety Monitoring Board (DSMB)

The responsibilities of the DSMB, composed of medical monitors (physicians experienced in oncology studies) and at least one statistician, are to review and evaluate the data for safety, study conduct and progress, and make recommendations concerning the continuation, modification, or termination of study. Serial assessments of PK results also may be taken into account for safety evaluation. A neurologist will be invited to join DSMB meeting as a consultant when neurotoxicity occurred.

The document review or meeting of DSMB will be held when the following scenarios:

- A subject is not recovered from Grade 2 neurotoxicity over three weeks;
- A subject revealed Grade 3 or above neurotoxicity;
- After 10 evaluable subjects finished the study in Stage I;

The schedule of assessments is shown in detail in [Table 1](#), [Table 2](#) and [Table 3](#). The results of protocol specific assessments and procedures will be recorded in the source documents for the subjects and on the appropriate page of the case report form (CRF). The different study days are described below.

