8.2. Determination of Sample Size

Assumption of sample size calculation:

- Study design: Simon's optimal two stage design¹
- Type I error (one-sided): 5%
- Power: 80%
- Response probability of null hypothesis (P0): 0.05
- Response probability of SCB01A (P1): 0.20

According to these hypotheses, up to 37 subjects need to be recruited into the study (including 10 evaluable subjects in the Stage I and 19 evaluable subjects in Stage II, with the additional 8 subjects to account for replacement of subjects those who withdraw, i.e. dropout rate is 20%). At least 4 subjects are required to achieve CR or PR after treatment with SCB01A for the study to meet its primary objective. The trial will be discontinued if no objective response is observed after the Stage I tumor assessment review.

Stopping rule: The study will be stopped early for futility if less than 1/10 evaluable subjects showed ORR in Stage I; with no further investigation of the drug is less than 4/29 evaluable subjects achieve ORR by the end of Stage II.

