8.3. Populations for Analysis

Subjects will be categorized into the following populations for analysis:

ITT population: The ITT population consists of all subjects enrolled in the study and received at least one study treatment.

Per-protocol (PP) population: The PP population will consist of all subjects who completed at least 3 cycles of study treatment regimen, have measurable baseline disease and at least one post-baseline RECIST assessment (PD, SD, PR or CR). Subjects with a major protocol violation, or AE, deemed by the Medical Monitor to have an impact on the study endpoints will be excluded from the PP population.

PK population: The PK population will consist of all subjects in stage I who received, at least, one dose of 24 mg/m² of SCB01A with sufficient post-dose bio-samples collected for PK profile characterization.

Details of any other populations for analysis will be described in the SAP.

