### 9.7.2 Determination of Sample Size

Assumption of sample size calculation:

- Study design: Simon's two stage design
- Type I error rate (one-sided): 5%
- Power: 80%
- Response probability of null hypothesis (P0): 0.05
- Response probability of SCB01A (P1): 0.20

According to these hypotheses, up to 37 subjects need to be recruited into the study (including 10 evaluable subjects in the Stage I and 19 evaluable subjects in Stage II, with the additional 8 subjects to account for replacement of subjects those who withdraw, i.e. dropout rate is 20%). At least 4 subjects are required to achieve CR or PR after treatment with SCB01A for the study to meet its primary objective. The trial would be discontinued if no objective response is observed after the Stage I tumor assessment review.

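### The per-protocol rule lets the Medical Monitor remove a subject because of an adverse event; that subject is then replaced in the set that decides efficacy, and one swapped non-responder takes exact type I error above 5%

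*SAP*

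**What the plan says.** **Exclusion.** SAP 9.7.1.1 removes from the PP population "Subjects with a major protocol deviation or AE, deemed by the Medical Monitor to have an impact on the study endpoints". The Protocol synopsis (Populations for Analysis) has the same sentence. Protocol 8.3 has nearly the same: "Subjects with a major protocol violation, or AE, deemed by the Medical Monitor to have an impact on the study endpoints". None of the three says what makes an AE count, when the judgement is made, or whether the Medical Monitor knows the subject's response.

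**Replacement.** The synopsis (Trial Design) states: "Per-protocol (PP) subjects will be considered to be evaluable for ORR conclusion; Non-evaluable subjects will be replaced". The synopsis entry on planned numbers also provides for replacing non-PP subjects.

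**Deciding set.** The synopsis and SAP 9.7.1.2 report efficacy on both ITT and PP and base the conclusion on PP. Protocol 4.10 confirms that the trial is open-label.

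**Decision rule.** Protocol 8.2 and SAP 9.7.2 require at least 4 responders, and Protocol 8.2 puts this as 4 of 29 evaluable subjects. The trial stops if none of the 10 evaluable Stage I subjects responds. Up to 37 are recruited, 8 of them as replacements.

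**Toxicity.** In the synopsis and SAP 9.7.1.1, limb (1) of the PP definition admits subjects who withdraw for a DLT. Limb (2) admits those with three completed cycles, measurable baseline disease and a post-baseline RECIST assessment. Section 8.3 has only the second limb. Protocol 3.1 makes a subject non-evaluable for receiving fewer than three cycles unless the cause is study-drug toxicity. The synopsis and SAP 9.8 count DLT withdrawals as non-responders, and SAP 9.8 does the same for tumor non-evaluable subjects.

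**The concern.** An AE on treatment is an outcome of the drug, unlike an eligibility or dosing error. Letting an AE take a subject out of the deciding set conditions the primary analysis on what the treatment did. The judgement is open-ended, and nothing in the text keeps it apart from the response data.

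Replacement makes this worse. If a non-responder is removed and another subject enrolled, the PP set still shows 29 while more than 29 have been treated, and each replacement is a further chance of response. The success rule is a small fixed count, so extra chances act directly on the type I error. Efficacy could then be declared against a nominal 5% that the procedure no longer delivers, with some subjects harmed by the drug missing from the denominator.

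The sentence also sits badly with the one before it. A DLT is an AE, so limb (1) admits DLT withdrawals while the exclusion sentence can take them out again, and no order of precedence is given.

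**Working it through.** **Inputs.** Protocol 8.2: "Study design: Simon's optimal two stage design". SAP 9.7.2: "Response probability of null hypothesis (P0): 0.05" and "Response probability of SCB01A (P1): 0.20". One-sided type I error is 5% and power 80%. There are 10 + 19 = 29 evaluable subjects. The synopsis gives 10–13 recruited in Stage I and 19–24 in Stage II.

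**Step 1: reproduce the plan.** With n1 and n2 subjects in the two stages,

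P(success) = Σ over x ≥ 1 of P(X1 = x) × P(X2 ≥ 4 − x), where X1 ~ Bin(n1, p) and X2 ~ Bin(n2, p).

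For n1 = 10, n2 = 19, p = 0.05:

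- x = 1: 0.31512 × 0.06655 = 0.02097
- x = 2: 0.07463 × 0.24529 = 0.01831
- x = 3: 0.01048 × 0.62265 = 0.00652
- x ≥ 4: 0.00103
- Sum: 0.0468

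At p = 0.20 the same formula gives 0.801. A search for the smallest expected sample size under the null, with error at most 5% and power at least 80%, returns this same design. Dropout also reproduces: 29/0.8 = 36.25, so 37; 10/0.8 = 12.5, so 13; 19/0.8 = 23.75, so 24. The design is sound as stated. Its slack is 5.0% − 4.7% = 0.3 percentage points.

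**Step 2: remove and replace known non-responders.** If k1 non-responders are swapped in Stage I and k2 in Stage II, the PP responder count equals the count among 10 + k1 and 19 + k2 treated subjects. The thresholds stay at 1 and 4. Putting those sizes into the formula at p = 0.05:

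| Swaps (k1 + k2) | Treated, Stage I / total | Type I error |
|---|---|---|
| 0 | 10 / 29 | 0.0468 |
| 0 + 1 | 10 / 30 | 0.0513 |
| 1 + 0 | 11 / 30 | 0.0532 |
| 1 + 1 | 11 / 31 | 0.0581 |
| 1 + 2 | 11 / 32 | 0.0631 |
| 2 + 3 | 12 / 34 | 0.0761 |
| 3 + 5 | 13 / 37 | 0.0966 |

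For the last row the terms are 0.04072 + 0.03762 + 0.01515 + 0.0031 = 0.0966. The chance of passing Stage I under the null rises from 1 − 0.95^10 = 0.401 to 1 − 0.95^13 = 0.487. Four responders would read as 4/29 = 13.8% in PP and 4/37 = 10.8% among all treated.

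**Step 3: whom the clause can reach.** A subject who stops before three cycles for an AE that is not a DLT is already outside PP, because limb (2) fails. The AE ground therefore adds two groups: DLT withdrawals admitted by limb (1), and subjects with three cycles and a post-baseline scan.

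**Step 4: set the toxicity rules side by side.** Take a subject who leaves in cycle 2 with a DLT.

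- Synopsis and SAP 9.7.1.1, limb (1): in PP, counted as a non-responder.
- The exclusion sentence that follows: may be removed from PP, hence replaced under the synopsis.
- Section 8.3: not in PP, since three cycles were not completed.
- Section 3.1: not made non-evaluable by the short treatment, so not replaced on that ground.

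These cannot all be followed.

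**The case against.** The strongest reply is that the plan already protects the denominator. DLT withdrawals count as non-responders, SAP 9.8 treats tumor non-evaluable subjects as failures, Section 3.1 does not replace subjects for short treatment due to study-drug toxicity, and ITT is reported. These are real protections, and it would be wrong to say that drug harm is simply taken out of the efficacy denominator. They are partial. SAP 9.8 says how a response is scored and names no analysis set. It does not cover a scanned subject with SD or PD who is removed for an AE. ITT does not decide, and no success count is given for more than 29 subjects. Reading limb (1) as the specific rule that prevails is reasonable, but the text does not say so, and Section 8.3 has no such limb.

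Second, a reader might take 9.7% as the trial's type I error. It is a ceiling. The 8 places are budgeted for withdrawals generally, so ordinary dropouts use them too, and the clause could also remove responders.

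Third, swapping needs the exclusion to fall during enrolment. If it is made only at a review before database lock, no replacement follows and PP falls below 29. The documents do not give the timing, so this tempers the concern without removing it.

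Fourth, the SAP text supplied starts mid-sentence and refers to a separate detailed SAP, where criteria might stand. The statement that no criterion exists holds only for the text supplied.

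Finally, a reader might infer that the person making exclusions sees the Stage I responses, because Protocol 3.1 describes the DSMB as "composed of medical monitors (physicians experienced in oncology studies) and at least one statistician". That is a general description of the board. Nothing identifies its members with the Medical Monitor of the PP rule, and the point does not rely on it.

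**Conclusion.** The concern holds. An AE-based, discretionary exclusion governs the set that decides the primary endpoint, and excluded subjects are replaced in an open-label trial. If the removed subjects are known non-responders and each is replaced, one swap is enough to exceed 5% (5.1% in Stage II, 5.3% in Stage I). Three swaps, one in Stage I and two in Stage II, give 6.3%. The maximum is 9.7%, about twice the design value, and needs all 8 replacement places spent this way.

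The documents show that such swaps are possible. They do not show that any was made or intended. The 5 subjects whom SAP 9.8 reports as not evaluated are no evidence of it: they are to be scored as non-responders, although their place in the PP denominator is left unstated.

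Apart from the size, the evaluable definitions in the synopsis, Protocol 3.1 and 8.3, and SAP 9.7.1.1 and 9.8 disagree on toxicity withdrawals and must be reconciled.

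**What to change.** 1. Delete *or AE* from the PP exclusion in the synopsis, Protocol 8.3 and SAP 9.7.1.1.
2. Limit exclusions to a short closed list of major protocol deviations, each decided without knowledge of that subject's response. A blinded judgement is preferable to a deadline before the first scan, which could not cover deviations that arise later, for example before the confirmatory scan.
3. Do not replace a subject whose post-baseline response has been read.
4. Reconcile the synopsis, Protocol 3.1 and 8.3, and SAP 9.7.1.1 and 9.8 into one definition of evaluable, in which treated subjects who leave for toxicity stay in the deciding denominator as non-responders. Step 1 alone would not do this, because early AE withdrawals without a DLT still fail the three-cycle limb.
5. List every PP exclusion with its reason, date and response, beside the ORR in all treated subjects.

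The SAP text is largely in the past tense. If enrolment has closed, replacement can no longer be changed, but the listing and the all-treated ORR can still be produced. As a yardstick for reading that ORR, with all 37 treated (13 + 24) the same formula gives a type I error of 0.097 for at least 4 responders, and 0.033 with power 0.858 for at least 5.

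The cost is wording and one listing. The PP ORR may be slightly lower, because some subjects with AEs stay in as non-responders.

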#### 9.7.1.2 Statistical Analysis

Both ITT and PP approaches would be included in the efficacy analyses. The efficacy conclusion would be summarized according to analyses of PP population. Safety analysis would be done on ITT population. Inferential analysis results would be expressed as point estimates and their 95% confidence intervals (CIs). Analyses would be carried out using SAS® Software, version 9.4 or higher (SAS Institute, Cary, North Carolina, USA).

All time-to-event endpoints, including OS and PFS, would be reported in days (median with 95% CI and range) and calculated using Kaplan-Meier methods. Subjects who have not progressed or who have not died at the time of the analysis would be censored at the last assessment date.

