
 • ORR is defined as the percentage of subjects who have achieved confirmed CR and PR during treatment phase, according to RECIST v1.1. Not-confirmed CR or PR, or withdraw for DLT are counted as non-responder. • PFS is defined as the time from the start of treatment up to the date of first progression based on RECIST v1.1 or the date of death, whichever comes first. • OS is defined as the time from the start of treatment up to the time that the subject is still alive. • Best overall tumor response defined as the best response from start of treatment through all treatment phase or until disease progression/recurrence. 
Survival data will be collected throughout the active treatment phase and during the 27 weeks follow-up period. Survival follow-up after subject discontinuation of treatment will be conducted every 3 weeks during the first 9 weeks, thereafter every 9 weeks until the end of the study to assess for survival. Survival rate will only be assessed in subjects with measurable disease at baseline.
 
Dose Limiting Toxicity (DLT):
 
All toxicities will be classified according to the National Cancer Institute (NCI) Common Terminology Criteria for AEs (CTCAE) version 4.03. DLT will be defined as the occurrence of any of the following criteria unless there is definitive alternative evidence that administration of SCB01A did not cause the specific toxicity:
 
 • Grade 4 neutropenia exceeding 5 days' duration; • Grade 4 thrombocytopenia; • Grade 4 anemia; • Grade 3 or greater neutropenia with complications (e.g., fever, infection etc.); • Grade 3 or greater thrombocytopenia with complications (e.g., bleeding); • Grade 3 or greater non-hematological AEs including Grade 3 unmanageable nausea and vomiting that persist for 3 or more days after drug administration. Grade 3 fatigue lasting for ≤ 1 week is not considered as a DLT; • Grade 3 or greater prolonged QTc interval; • Grade 3 or greater neurotoxicity; • Delayed treatment exceeding 14 days duration due to drug-related toxicity; • Not able to recover from grade 2 neurotoxicity exceeding 3 weeks. 
Safety measurements:
 
The following safety assessments will be done during the study:
	

Name of Sponsor/Company: SynCore Biotechnology Co. Ltd.	
Name of Study Product: SCB01A	
Protocol Number: SCB01A-22	Indication: Recurrent or metastatic squamous cell carcinoma of head and neck

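### PFS and OS are timed from first dose but concluded on a per-protocol set entered mainly by completing 3 cycles, which biases the PP Kaplan-Meier estimates upward

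*SAP*

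**What the plan says.** **Clock.** The protocol synopsis (Criteria for Evaluation) gives "PFS is defined as the time from the start of treatment up to the date of first progression", or to death if that is earlier. OS has the same origin. Protocol 6.1 repeats both origins.

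**Method.** SAP 9.7.1.2 and protocol 8.5 use Kaplan-Meier medians with 95% CIs. Neither describes a landmark or delayed entry.

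**Population.** SAP 9.7.1.2 includes both ITT and PP efficacy analyses, then adds: "The efficacy conclusion would be summarized according to analyses of PP population". The synopsis says the same. Protocol 8.5 lists PFS and overall survival among the secondary efficacy analyses.

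**Entry to PP.** Under SAP 9.7.1.1 and the synopsis there are two routes. One is withdrawal for DLT. The other is for subjects who "completed at least 3 cycles of study treatment regimen, have measurable baseline disease" and have at least one post-baseline RECIST assessment, which may be PD. Protocol 8.3 gives only the second route.

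**Early leavers.** Protocol 3.1 ends treatment at progression or death. It treats subjects with under 9 weeks (3 cycles) of drug as non-evaluable for ORR, unless the reason was drug toxicity, and replaces them.

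**The concern.** Completing 3 cycles happens after the clock has started. A subject who dies in Cycle 1 or 2 without having been withdrawn for DLT cannot be in PP, whereas a subject who gets through 3 cycles enters with that time already credited. This is immortal-time (survivor) selection, and it lengthens the PP curves whatever the drug does.

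Such subjects exist. The ORR note in SAP 9.8 reports 5 subjects not evaluated because of clinical progression or AE/SAE and calls such subjects likely treatment failures. It counts them as non-responders for ORR but says nothing about PFS or OS, where a subject without a post-baseline assessment leaves PP unless the DLT route applies.

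The trial has no control group (protocol 3.6), so there is no second arm carrying the same selection against which it could cancel.

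**Working it through.** **The plan's own figures.** The documents give no median, event count or power for PFS or OS, so there is nothing of that kind to reproduce. The sample size does reproduce. It takes "Response probability of null hypothesis (P0): 0.05", "Response probability of SCB01A (P1): 0.20" and "10 evaluable subjects in the Stage I and 19 evaluable subjects in Stage II", continues on at least 1/10 and succeeds on at least 4/29. The exact one-sided alpha is 0.0468 and the power 0.8011; 29/0.8 = 36.25, rounded up to 37. The design is sound for ORR and does not bear on the time-to-event endpoints.

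**Threshold L for entry to PP.** Cycles last 21 days, so 3 × 21 = 63 days, which agrees with the 9 weeks in protocol 3.1. If "completed" means only that the last Cycle 3 infusion was given, Table 1 puts that at Day 50. So L lies between 50 and 63 days.

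**OS.** Assume exponential survival with true median m, so S(t) = 2^(−t/m). Assume also that every subject without a DLT withdrawal who is alive at L enters PP.

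- *No DLT route (protocol 8.3).* The PP curve is S(t)/S(L) for t ≥ L, so the PP median is m + L, a shift of 50 to 63 days. For m = 180 it is 230 (L = 50) or 243 (L = 63).
- *15% of treated subjects exempt, L = 63.* The PP median solves S(t) = 0.5 × [0.15 + 0.85 × S(63)]. With S(63) = 2^(−0.35) = 0.785, the right side is 0.408 and t = 180 × 1.292 = 232.5, about 233 days (+53).
- *DLT share w of the PP set.* The PP median is t = m × log2{2 × [w + (1 − w)/S(L)]}. For m = 180:

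| w | L = 50 | L = 63 |
|---|---|---|
| 0 | 230 | 243 |
| 0.1 | 225 | 237 |
| 0.2 | 221 | 232 |
| 0.3 | 216 | 226 |

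The smallest shift is at L = 50 and w = 0.3: 216 − 180 = 36 days. True medians of 120 and 240 days give about the same there (156 and 276).

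*Cross-check from the plan's own allowance.* Suppose the 8 of 37 replaced subjects all have their events before the PP median. That median is then read where all-treated survival is 0.5 × 29/37 = 0.392, and −log2(0.392) = 1.35, so it is about 35% too long (180 becomes 243). Replacement for other reasons would give less.

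**PFS.** Adding L to the median is the wrong model here. PP admits a post-baseline PD, and the first scheduled scan is at the end of Cycle 3, about Day 64 (Table 1, footnote 5). The next is before Cycle 7 Day 1, which is 6 × 21 + 1 = Day 127. Let q be the share of progressions before Day 63 that are found early and end treatment (assumed). The rest are recorded at Day 64 and stay in PP. PP survival at a scan day t is S(t)/[1 − q × (1 − S(63))].

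- *q = 0:* ITT and PP are identical.
- *m = 90, q = 0.5:* 1 − S(63) = 0.384. ITT is 0.611 at Day 64 and 0.376 at Day 127, so its median is 127. PP at Day 127 is 0.376/0.808 = 0.465, so its median is also 127. No shift.
- *m = 63, q = 0.25:* ITT at Day 64 is 0.4945, median 64. PP is 0.4945/0.875 = 0.565 at Day 64 and 0.247/0.875 = 0.283 at Day 127, median 127. The shift is one scan interval, 63 days.

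The shift goes somewhat beyond one interval only in the extreme where q = 1 and the true median is short. At m = 45 the ITT median is then 45, and PP survival at Day 127 is 2^(−64/45) = 0.373, so the PP median is 127.

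**The case against.** A reader might infer that the PP curves carry nine weeks of guaranteed event-free time, and that both medians are inflated by 63 days. The documents do not support that, for three reasons:

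- The SAP and synopsis admit subjects withdrawn for DLT at any time, so early events can occur in PP. Only protocol 8.3 lacks that route.
- "Completed" is not defined and could be met near Day 50.
- Progression first seen on the end-of-Cycle-3 scan stays in PP. With no earlier scheduled scan, the ITT curve for PFS will also be fairly flat to about Day 64. That part comes from the scan schedule, and changing the population does not remove it.

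Two further points have weight. ITT analyses are planned and all subjects are followed for survival, so medians free of this selection will exist; the fault lies in which set carries the conclusion. And the conclusion sentence may have been meant for ORR: the synopsis (Trial Design) ties PP to the ORR conclusion, and only ORR has a decision rule. But SAP 9.7.1.2 does not limit the sentence to ORR, and protocol 8.5 calls PFS and OS efficacy analyses. Read as written, it covers them.

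Finally, the SAP text supplied is an extract that refers to a more detailed SAP. A landmark rule or a separate time-to-event population could be there; none appears in the text at hand.

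**Conclusion.** The concern holds for the PP estimates, and most clearly for OS, which does not depend on scans. Under exponential survival the PP median OS is too long by about 50 to 63 days with no DLT route. The shift is smaller with one: about 53 days for a true median of 180 with 15% exempt and a Day 63 threshold, and about 36 days at the low end of the range tried. For PFS the direction is upward, but the size cannot be fixed from the documents; it runs from none to about one scan interval, depending on how many early progressions are found before the first scheduled scan.

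The true medians, DLT share, early-detection share and exponential form are all assumptions. It would go too far to call every reported median biased in this way, since the ITT medians are free of this selection.

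**What to change.** 1. In SAP 9.7.1.2 and protocol 8.5, state that PFS and OS are estimated and concluded on the ITT (all treated) population. If the PP sentence was meant for ORR only, say so.
2. The synopsis limits the survival assessment to subjects with measurable disease at baseline; protocol 6.1 does not repeat this. Decide whether it is intended. If so, keep it: it is a baseline condition and does not create this bias.
3. Show any PP curve only as a landmark analysis from the end of Cycle 3, in subjects still event-free then, with time counted from the landmark and the figure labelled accordingly.
4. Reconcile the two PP definitions (protocol 8.3 against the synopsis and SAP 9.7.1.1), and define completion of 3 cycles by a study day or visit.

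The cost is a few sentences. No new data are needed, because the ITT curves are already planned. The stated medians may become less favourable.
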